#### 1.4.1 Preclinical Experience

Please refer to the current pomalidomide Investigator's Brochure (IB).

#### 1.4.2 Clinical Experience

In Trial 1 in MM, data were evaluated from 219 patients (safety population) who received treatment with pomalidomide + low-dose dex (112 patients) or pomalidomide alone (107 patients). Median number of treatment cycles was 5. Sixty-seven percent of patients in the study had a dose interruption of either drug due to adverse reactions. Forty-two percent of patients in the study had a dose reduction of either drug due to adverse reactions. The discontinuation rate due to adverse reactions was 11%.

The table below summarizes the analysis results of overall response rate (ORR) and duration of response (DOR), based on assessments by the Independent Review Adjudication Committee for the treatment arms in Trial 1. ORR did not differ based on type of prior antineoplastic therapy.

	Pomalidomide (m=108)	Pomalidomide + Low-dose Dex (n=113)
Response	8 (7.4)	33 (29.2)

Overall Response Rate, %	(3.3, 14.1)	(21.0, 38.5)
Complete Response Rate %	0 (0.0)	1 (0.9)
Partial Response %	8 (7.4)	32 (28.3)
Duration of Response (DOR) Median, months	NE	7.4
95% CI for DOR (months)	NE	(5.1, 9.2)

In Trial 2, data were evaluated from 450 patients (safety population) who received treatment with pomalidomide + low-dose dex (300 patients) or high-dose dexamethasone (high-dose dex) (150 patients). The median number of treatment cycles for the pomalidomide + low-dose dex arm was 5. In the pomalidomide + low-dose dex arm, 67% of patients had a dose interruption of pomalidomide, the median time to the first dose interruption of pomalidomide was 4.1 weeks. Twenty-seven percent of patients had a dose reduction of pomalidomide, the median time to the first dose reduction of pomalidomide was 4.5 weeks. Eight percent of patients discontinued pomalidomide due to adverse reactions.

The table below summarizes the progression free survival (PFS) and overall response rate (ORR) based on the assessment by the Independent Review Adjudication Committee (IRAC) review at the final PFS analysis and overall survival (OS) at the OS analysis. PFS was significantly longer with POMALYST + Low-dose Dex than High-dose Dex: HR 0.45 (95% CI: 0.35-0.59 p < 0.001). OS was also significantly longer with POMALYST + Low-dose Dex than High-dose Dex: HR 0.70 (95% CI: 0.54-0.92 p = 0.009). The Kaplan-Meier curves for PFS and OS for the ITT population are provided in Figures 1 and 2, respectively.

	Pomalidomide (m=302)	Pomalidomide + Low-dose Dex (n=153)
Progression Free Survival Time		
Median	3.6 [3.0, 4.6]	1.8 [1.6, 2.1]
Hazard ratio	0.45 [0.35, 0.59]	
Overall Survival Time		
Complete Response	1 (0.3)	0
Very Good Partial Response	8 (2.6)	1 (0.7)
Partial Response	62 (20.5)	5 (3.3)

### 1.4.3 Pharmacokinetics and Drug Metabolism

Pomalidomide is primarily metabolized by CYP1A2 and CYP3A4. Pomalidomide is also a substrate for P-glycoprotein (P-gp).

CYP1A2 inhibitors: In healthy volunteers, co-administration of fluvoxamine, a strong CYP1A2 inhibitor, increased Cmax and AUC of pomalidomide by 24% and 125% respectively. Increased pomalidomide exposure increases the risk of exposure related

toxicities. Avoid co-administration of strong CYP1A2 inhibitors (e.g. ciprofloxacin and fluvoxamine) and Clinical Pharmacology. If co-administration is unavoidable, reduce the pomalidomide dose.

In patients with multiple myeloma who received pomalidomide 4 mg daily alone or in combination with dexamethasone, pomalidomide steady-state drug exposure was characterized by AUC of 860 ng·h/mL (CV% =37%) and Cmax of 75 ng/mL (CV% = 32%).

Absorption: Following administration of single oral doses of pomalidomide, the maximum plasma concentration (Cmax) for pomalidomide occurs at 2 and 3 hours postdose.

Effect of Food Co-administration of pomalidomide with a high-fat meal (approximately 50% of the total caloric content) and high-calorie meal (approximately 800 to 1000 calories) (the meal contained approximately 150, 250, and 500 to 600 calories from protein, carbohydrates, and fat, respectively) delays the Tmax by 2.5 hours, decreased mean plasma Cmax and AUC in healthy volunteers by about 27% and 8%, respectively.

Distribution: Pomalidomide has a mean apparent volume of distribution (Vd/F) between 62 and 138 L at steady state. Pomalidomide is distributed in semen of healthy subjects at a concentration of approximately 67% of plasma level at 4 hours postdose (~Tmax) after 4 days of once-daily dosing at 2 mg. Human plasma protein binding ranges from 12% to 44% and is not concentration dependent. Pomalidomide is a substrate for P-gp.

Elimination: Pomalidomide has a mean total body clearance (CL/F) of 7-10 L/h. Pomalidomide is eliminated with a median plasma half-life of approximately 9.5 hours in healthy subjects and approximately 7.5 hours in patients with multiple myeloma.

Metabolism: Pomalidomide is primarily metabolized in the liver by CYP1A2 and CYP3A4. Minor contributions from CYP2C19 and CYP2D6 were also observed in vitro.

Following a single oral administration of [14C]-pomalidomide to healthy subjects, approximately 73% and 15% of the radioactive dose was eliminated in urine and feces, respectively, with approximately 2% and 8% of the radiolabeled dose eliminated unchanged as pomalidomide in urine and feces.

### Specific Populations

Age (61 to 85 years old), sex and race had no clinically significant effect on the systemic exposure of pomalidomide. The pharmacokinetics of pomalidomide is unknown in pediatric patients.

Renal Impairment: Pomalidomide pharmacokinetic parameters were not significantly affected in patients with moderate ( $30 \text{ mL/min} \leq \text{CrCL} < 60 \text{ mL/min}$ ) or severe ( $15 \text{ mL/min} \leq \text{CrCL} < 30 \text{ mL/min}$ ) renal impairment relative to patients with normal renal function ( $\text{CrCL} \geq 60 \text{ mL/min}$ ). Mean exposure (AUC) to pomalidomide increased by 38% in patients with severe renal impairment requiring dialysis ( $\text{CrCL} < 30 \text{ mL/min}$  requiring dialysis) and 40% in patients with end stage renal disease ( $\text{CrCL} < 15 \text{ mL/min}$ ) on non-dialysis days. In patients with severe renal impairment requiring dialysis, the estimated dialysis clearance is approximately 12 L/h which is higher than pomalidomide total body clearance, indicating hemodialysis will remove pomalidomide from the blood circulation.

Hepatic Impairment: Mean exposure (AUC) increased by 51%, 58% and 72% in subjects with mild, moderate or severe hepatic impairment as defined by Child-Pugh criteria, respectively.

### Drug Interaction Studies

Co-administration of pomalidomide with the following drugs did not increase pomalidomide exposure to a clinically significant extent: ketoconazole (a strong CYP3A4 and P-gp inhibitor), carbamazepine (a strong CYP3A4 inducer) and dexamethasone (a weak to moderate inducer of CYP3A4). Co-administration of pomalidomide with drugs that are CYP1A2 inducers has not been studied.

CYP1A2 Inhibitors: Co-administration of fluvoxamine (a strong CYP1A2 inhibitor) with pomalidomide increased mean [90% confidence interval] pomalidomide exposure by 125% [98% to 157%] compared to pomalidomide alone in healthy subjects. Co-administration of fluvoxamine in the presence of ketoconazole (a strong CYP3A4 and P-gp inhibitor) with pomalidomide increased mean pomalidomide exposure by 146% [126% to 167%] compared to pomalidomide administered alone in healthy subjects, indicating the predominant effect of CYP1A2 inhibition in the increase of pomalidomide exposure.

Strong CYP3A4 and P-gp Inhibitors: Co-administration of ketoconazole (a strong CYP3A4 and P-gp inhibitor) in 16 healthy male subjects increased AUC of pomalidomide by 19% compared to pomalidomide administered alone.

#### Drugs that Induce Pomalidomide Metabolism

Strong CYP1A2 Inducers: Co-administration of pomalidomide with drugs that are CYP1A2 inducers has not been studied and may reduce pomalidomide exposure.

Strong CYP3A4 Inducers: Co-administration of carbamazepine to 16 healthy male subjects decreased AUC of pomalidomide by 20% with a 90% confidence interval [13% to 27%] compared to when pomalidomide was administered alone.

Dexamethasone: Co-administration of multiple doses of 4 mg pomalidomide with 20 mg to 40 mg dexamethasone (a weak to moderate inducer of CYP3A4) to patients with multiple myeloma had no effect on the pharmacokinetics of pomalidomide compared to when pomalidomide was administered alone.

Smoking: In 14 healthy male subjects who smoked 25 cigarettes per day for a total of 10 days, after single oral dose of 4 mg pomalidomide, Cmax of pomalidomide increased 14% while AUC of pomalidomide decreased 32%, compared to that in 13 healthy male volunteers who were non-smokers.

#### In Vitro Studies

Pomalidomide does not inhibit or induce CYP450 enzymes or transporters in vitro.

## **2. STUDY OBJECTIVES**

### **2.1 Primary Objectives**

- To determine best response within 8 cycles of treatment with daratumumab, clarithromycin, pomalidomide, and dexamethasone (D-ClaPd) in patients with multiple myeloma.

### **2.2 Secondary Objectives**

To determine:

- Median PFS
- Overall survival
- Time to response
- Time to progression
- Duration of response
- Time to next therapy
- Overall response rate
- Complete response rate
- VGPR response rate
- Exploratory Endpoints and Correlative Studies (see Section 3.3)

## **3. STUDY ENDPOINTS**

### **3.1 Primary Endpoints**

- $\geq$  VGPR response proportion as best response within 8 cycles of induction treatment

### **3.2 Secondary Endpoints**

- PFS
- Overall survival
- Time to response
- Time to progression
- Duration of response
- Time to next therapy
- Complete response rate or better
- Overall response rate (responses  $\geq$  PR)
- VGPR response rate or better
- MRD negativity rate
- Improvement in response rate during maintenance therapy

### **3.3 Exploratory Endpoints and Correlative Studies**

There will be numerous correlative studies incorporated into the main study as exploratory endpoints. These will include monitoring for response assessment by imaging studies as well as MRD by multiparameter flow cytometry (MFC), FISH, and NGS. MFC-based tests of immune cells from marrow will be studied for various immune-based and daratumumab-based markers (see below). Samples obtained for correlative studies will be retained and may be stored for potential future use. The samples will be collected and stored in a de-identified manner, and only individuals associated with the protocol will have access to and/or handle the samples. The samples will be analyzed and/or stored at the main study site.

3.3.1 MFC of bone marrow aspirate at diagnosis and at best response for MRD using Euroflow-based panel (both time points)

3.3.2 NGS at diagnosis and at best response for MRD using NGS assays

3.3.3 MFC at diagnosis and at best response of bone marrow aspirate for immune cells and daratumumab-based markers (M1/M2, CD36, CD38, NK; CD55/59)

3.3.4 Imaging (PET/MRI) at diagnosis and at best response/MRD

3.3.5 Dose intensity analysis (mean relative dose intensity of dexamethasone)

## 4. STUDY DESIGN

### 4.1 Overview of Study Design

This is a single center, single-arm phase 2 study that will be conducted at Weill Cornell Medical College to evaluate the best response within 8 cycles of induction in relapsed/refractory multiple myeloma compared to historical pomalidomide/dexamethasone. Patients will receive daratumumab/clarithromycin/ pomalidomide/dexamethasone (D-ClaPd) for 8 cycles of induction followed by daratumumab/pomalidomide/dexamethasone for maintenance until PD or unacceptable toxicity, whichever comes first. Patients will be treated for up to 24 months of maintenance if evidence of PR or better after induction.

D-ClaPd has potential for synergistic activity with good tolerability/safety in relapsed/refractory myeloma.

In patients with previous daratumumab exposure, the following hypotheses will be tested:

- D-ClaPd will yield higher  $\geq$ VGPR rates in relapsed/refractory myeloma than historical pomalidomide/dexamethasone ( $\geq$ VGPR 9%) in this setting.
- Daratumumab retreatment in combination with ClaPd in early relapse will have higher ORR than ClaPd (ORR 60%).

Patient participation will include a screening phase and a treatment phase. The screening phase will be up to 28 days prior to first dose of study drug. The Treatment Phase begins on the date of the first study treatment and ends on the date the patient and the investigator agree that the patient will no longer continue study treatment.

During the treatment phase, daratumumab, clarithromycin, pomalidomide, and dexamethasone will be administered as per the following schedule.

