## Protocol Summary

Full Title:	A PHASE II STUDY OF DARATUMUMAB, CLARITHROMYCIN, POMALIDOMIDE AND DEXAMETHASONE (D-ClaPd) IN MULTIPLE MYELOMA PATIENTS PREVIOUSLY EXPOSED TO DARATUMUMAB
Short Title:	D-ClaPd IN REL/REF MULTIPLE MYELOMA
Clinical Phase:	2
Principal Investigator:	[name] [name]
Study Description:	This single-arm phase 2 study will test the hypothesis that in patients with previous daratumumab exposure, daratumumab in combination with ClaPd will yield higher $\geq$ VGPR rates in historical pomalidomide/dexamethasone.
Sample Size:	N= 40
Enrollment:	This study will enroll 40 subjects and screen up to 44 subjects.
Study Population:	Patients will be over 18 years of age with relapsed/refractory multiple myeloma. Patients who have received 1 or more prior lines of therapy which must include daratumumab and may include ASCT are eligible. The patient must have received both an IMiD and PI in prior lines. Prior pomalidomide exposure in 1 or more previous lines of therapy allowed if PR or better achieved. No disease progression may have occurred within 60 days of receiving pomalidomide. Patient may be daratumumab refractory (i.e less than a PR) achieved on prior daratumumab-based therapy or have exhibited progression within 60 days of receiving daratumumab.
Study Design:	This is a single-center single-arm phase 2 study in which 40 patients will receive daratumumab in combination with clarithromycin/pomalidomide/dexamethasone until PD or unacceptable toxicity, whichever comes first. Patients will be treated for 8 cycles of therapy with continuation of maintenance daratumumab/pomalidomide if evidence of PR or better.

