## 4.3 Duration of Study

Patients will receive D-ClaPd at a dose defined by the treatment plan for up to 30 cycles, unless one of the following occurs:

- Disease progression
- Intercurrent illness that prevents further administration of treatment
- Unacceptable adverse event(s) defined as:

Occurrence of an AE that is related to treatment with the study drug which, in the judgment of the investigator, compromises the patient's ability to continue study-specific procedures, or is considered to not be in the patient's best interest.

Persistent AE requiring a delay of therapy for more than 4 weeks (28 days).

- Patient decides to withdraw from the study
- General or specific changes in the patient's condition render the patient unacceptable for further treatment in the judgment of the investigator
- Patient becomes pregnant
- Patient loses the ability to freely provide consent through imprisonment or involuntary incarceration for treatment of a psychiatric or physical illness
- Patient achieves complete remission (CR), and the patient and investigator feel that discontinuation is in the patient's best interests, or
- Patient achieves a level of response that qualifies him or her for another therapy, such as high dose therapy with autologous stem cell transplantation, and the patient and investigator feel that discontinuation is in the patient's best interests

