### **6.11 Termination of Treatment and/or Study Participation**

Patients will receive DPd at a dose defined by the treatment plan for up to 12 cycles, unless one of the following occurs:

- Hematologic disease progression.
- Intercurrent illness that prevents further administration of treatment
- Unacceptable adverse event(s) defined as:
  - o Occurrence of an AE that is related to treatment with the study drug which, in the judgment of the investigator, compromises the patient's ability to continue study-specific procedures, or is considered to not be in the patient's best interest.
  - o Persistent AE requiring a delay of therapy for more than 4 weeks (28 days).
- Patient decides to withdraw from the study
- General or specific changes in the patient's condition render the patient unacceptable for further treatment in the judgment of the investigator
- Patient becomes pregnant
- Patient loses the ability to freely provide consent through imprisonment or involuntary incarceration for treatment of a psychiatric or physical illness
- Patient achieves complete remission (CR), and the patient and investigator feel that discontinuation of DPd is in the patient's best interests, or
- Patient achieves a level of response that qualifies him or her for another therapy, such as high dose therapy with autologous stem cell transplantation, and the patient and investigator feel that discontinuation of DPd is in the patient's best interests.

Patients will be informed that they have the right to withdraw from the study at any time for any reason, without prejudice to their medical care. At the time of withdrawal, all study procedures outlined for the End of Study visit should be completed. The

primary reason for patient's withdrawal from the study should be recorded in the source documents and CRF.

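### The condition that maintenance requires PR or better after cycle 8 is missing from the stopping lists and dosing schedules, so a non-progressing patient below PR stops under one rule and continues under the other

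*Combined protocol and SAP*

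**What the plan says.** Two places make maintenance depend on response. The Protocol Summary (Study Design) says: "Patients will be treated for 8 cycles of therapy with continuation of maintenance daratumumab/pomalidomide if evidence of PR or better". Section 4.1 says: "Patients will be treated for up to 24 months of maintenance if evidence of PR or better after induction".

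The other places set no such condition:

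- The sentence in Section 4.1 just before the gate describes the three-drug combination "for maintenance until PD or unacceptable toxicity, whichever comes first".
- Section 4.3 opens its stopping list with: "Patients will receive D-ClaPd at a dose defined by the treatment plan for up to 30 cycles, unless one of the following occurs". The list covers progression, intercurrent illness, unacceptable adverse events, withdrawal, a change in the patient's condition, pregnancy, loss of free consent, CR with agreed discontinuation, and a response that qualifies the patient for another therapy. It has no item for a response below PR after induction.
- Section 6.11 opens with: "Patients will receive DPd at a dose defined by the treatment plan for up to 12 cycles, unless one of the following occurs". It then gives essentially the same list, again without such an item.
- The maintenance block in the Protocol Summary, the Schedule of Study Procedures and the cycle 9-30 schedule under Section 4.1 give doses and days only.

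One secondary endpoint in Section 3.2 depends directly on who enters maintenance: "Improvement in response rate during maintenance therapy". Neither Section 3.2 nor Section 8.1 gives its denominator.

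**The concern.** The documents never say what happens to a patient with stable or minimally improved disease at the end of cycle 8. The gate is stated in the design overview, but the sections that govern duration and termination do not list it. Staff working from Section 4.3, Section 6.11 or the calendar would find no instruction to stop such a patient. Staff working from the Summary or from the gating sentence of Section 4.1 would find one.

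The two paths lead to different treatment exposure, different disease-assessment schedules and different membership of the maintenance-phase population. Several secondary endpoints are computed from exactly those things. If patients are handled inconsistently, the analysis cannot undo it afterwards.

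**Working it through.** **1. Is the primary analysis touched?** Section 8.1.1 gives N = 40, success at 8 or more patients with VGPR or better, a null rate of 9% and a target rate of 25%. With X binomial:

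- P(X >= 8 | n = 40, p = 0.09) = 0.0242, so the probability of a negative result is 0.976. The plan states at least 0.95.
- P(X >= 8 | n = 40, p = 0.25) = 0.818. The plan states at least 0.80.

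The stated bounds hold. Section 3.1 fixes the endpoint as best response within 8 cycles, so the handling of patients after cycle 8 cannot change it.

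**2. The passages side by side.** Take a patient with stable disease at the end of cycle 8, no progression and no other listed stopping event.

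| Place | Response condition for cycle 9 onward | Result for this patient |
|---|---|---|
| Protocol Summary, Study Design | PR or better | Stops |
| Section 4.1, gating sentence | PR or better | Stops |
| Section 4.1, preceding sentence | None | Continues |
| Cycle 9-30 schedule; Summary maintenance block; calendar | None | Continues |
| Section 4.3 list | None | Continues |
| Section 6.11 list | None | Continues, to a 12-cycle limit |

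The lists do use response as a criterion: progression at one end, CR or transplant-qualifying response at the other. The band between progression and PR is the one left out. The nearest discretionary item is a change in condition that would "render the patient unacceptable for further treatment in the judgment of the investigator". That is not a response rule.

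**3. Exposure at stake.**

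- Section 4.3 and the schedule: cycles 9 to 30 are 22 cycles, and 22 x 28 = 616 days, or 616 / 30.4375 = 20.2 months.
- Section 6.11: 12 - 8 = 4 cycles, and 4 x 28 = 112 days, or 3.7 months.
- Under the gate: none.

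The disagreement over the cycle limit (12, 30, and 32 in the Summary and Section 7.4) is a separate inconsistency. Settling it would leave this one open.

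**4. Assessment frequency.** On treatment, the calendar has serum and urine disease tests every 28-day cycle (+/- 7 days for cycles 3-30). After stopping without progression, the patient has an end-of-treatment visit 90 days after the last dose, or earlier if new therapy is about to start (Section 7.3). Evaluations then follow every 90 +/- 30 days (Sections 4.3 and 7.4). Over the same 616 days:

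- continuing: 616 / 28 = 22 scheduled assessments;
- stopped: 616 / 90 = 6.8, so 6 completed nominal intervals.

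Progression can go undetected for up to a nominal 28 days in the first case and 90 in the second. The spread around 90 depends on how the window is read: 60 to 120 days if counted from the previous visit, 30 to 150 days if each visit floats around a fixed date. The documents do not say which. Section 8.1.6 censors PFS at the last disease assessment, so the grid also affects censoring times.

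**5. Denominator for improvement during maintenance.** Let m patients enter in PR or better, of whom k improve, and let s enter below PR, of whom j improve. With the gate the rate is k / m; without it, (k + j) / (m + s). Both numerator and denominator change.

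**6. How many patients?** Section 1.1 cites 11 patients refractory to daratumumab or pomalidomide, with ORR 54.6% (6 of 11) and clinical benefit 63.6% (7 of 11). The gap is 1 of 11, and 40 x 1/11 = 3.6. The exact 95% interval for 1 of 11 is about 0.2% to 41%, which is 0 to 16 of 40. The eight doubly refractory patients in the same section show 12.5% against 50.0%, a gap of 3 of 8, or 15 of 40 if scaled up. That group is less relevant because exclusion 1 bars progression within 60 days of pomalidomide.

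Neither gap measures the right quantity. Clinical benefit is not defined in the documents. The relevant group is patients both below PR and progression-free at day 8 x 28 = 224 (7.4 months), whereas the median PFS figures in Section 1.1 run from 3.7 to 8.8 months. The number cannot be derived.

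**The case against.** The best counter-argument is that the documents can be harmonised. The only two places that address response at the end of induction agree on PR or better. In both, the gate follows directly after the sentence on treating until progression or toxicity, so it can be read as qualifying that sentence. Section 4.3 gives a ceiling and refers to the treatment plan, and dosing schedules need not repeat entry conditions. This reading is plausible. But nothing in Section 4.3 or 6.11 says that the gate in Section 4.1 governs, and a list introduced as the set of exceptions invites the reader to treat it as complete. The omission therefore stands as a defect of wording.

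It is also fair to say that the impact is limited: the affected endpoints are secondary, are estimated in one arm, and carry no decision threshold.

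A reader might infer more than the text supports:

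- **That every non-progressing patient continues under Sections 4.3 and 6.11.** Both lists contain other stops, including toxicity, intercurrent illness and investigator judgment.
- **That such a patient would receive two further years of treatment.** Section 4.3 allows 616 days and Section 6.11 allows 112.
- **That stopped patients would start new therapy sooner.** Time to next therapy can depend on the rule, but the documents give no evidence of direction or size.
- **That the enrolling facilities will diverge.** Three are listed, but the study is described as single-center, and nothing suggests that they decide entry to maintenance independently.

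**Conclusion.** The inconsistency is real and minor. For a patient below PR but not progressing at the end of cycle 8, and with no other listed stop, the Protocol Summary and the gating sentence of Section 4.1 end treatment; the lists in Sections 4.3 and 6.11 and the schedules let it continue. The primary endpoint and the 8-of-40 rule are unaffected.

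PFS, time to progression, time to next therapy, maintenance-phase adverse events and improvement during maintenance can all depend on which rule is followed. For each such patient the difference is up to 616 days of treatment under Section 4.3 (112 under Section 6.11) and a nominal assessment interval of 28 against 90 days. The number of such patients is unknown; the 1-of-11 figure is too imprecise, and too indirect a measure, to support an estimate. The conclusion assumes only that the lists in Sections 4.3 and 6.11 are meant to be used as written. It takes no position on which rule is clinically right.

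**What to change.** Reconcile the Protocol Summary (Study Design and the maintenance block), the Schedule of Study Procedures, both sentences of Section 4.1, the cycle 9-30 schedule, and the lists in Sections 4.3 and 6.11, so that one rule for patients below PR at the end of cycle 8 appears throughout. Which rule that should be is for the sponsor to decide.

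Two further steps make the analysis follow the rule:

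- record each patient's response status at the cycle 8/9 boundary;
- define the denominator for improvement in response during maintenance, in Sections 3.2 and 8.1.6, as the patients who enter maintenance under the reconciled rule.

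No separate assessment schedule is needed for patients stopped by this rule; they can follow the same post-treatment schedule as others who stop before progression. The cost is a wording amendment and one recorded data item, based on tests already in the calendar. The sample size does not change. The amendment is best made before patients reach cycle 9.
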